9.3.3 Primary analysis

All pharmacokinetic results (e.g., PK parameters and plasma concentrations) will be summarized by dose and age group using appropriate graphs and descriptive statistics (i.e., number of patients (n), mean, standard deviation (SD), geometric mean, 95% confidence intervals, coefficient of variation (CV%), median, minimum, and maximum).

Relevant PK parameters (e.g., AUC, C_{max}) in children and adolescents will be descriptively compared to those in adults to demonstrate sufficient similarity of febuxostat pharmacokinetics.

The primary analyses will be conducted on the PK population and for exploratory reasons on the PP-PK population.

[figure not shown]

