As children and adolescents do not show any major differences in TLS diagnosis, management or treatment in respect of the adult population, the FLORENCE study results in adults strongly suggest that febuxostat could be of significant benefit also in children and adolescents. Starting from the assumption that the clinical condition of hyperuricemia in patients with hematological malignancies undergoing chemotherapy is similar between adults and children, it is reasonable to assume that the exposure-response (ER) relationship between the two populations could be similar. In this context, the present study aims at showing that the febuxostat exposure levels achieved in children and adolescents with the selected doses are similar to those achieved in adults receiving 120 mg febuxostat once daily. The proposed Pharmacodynamic (PD) assessment, namely AUC sUA Days 1-8, corresponds to the primary efficacy parameter which was evaluated in the phase III pivotal study FLORENCE in adults [8]. The Pharmacokinetic (PK) and PK/PD modeling and simulation analyses will apply to the PK and PD observed data in order to investigate the relationship between PK/PD and age as main covariate. Therefore, the efficacy and safety data collected in the pivotal phase III study FLORENCE in adults will be bridged to the pediatric population by solely PK, as well as by PK/PD analyses, showing a full matching of febuxostat drug exposure and exposure/response between the adult and pediatric populations.

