4) Febuxostat safety profile in adults has been broadly explored in the gout and TLS experience. In the clinical development for the gout indication, more than 4000 subjects received at least one febuxostat dose; more than 2500 subjects were exposed to febuxostat 80 mg, and more than 1000 to febuxostat 120 mg; and the mean duration of dosing in the 80 mg and 120 mg groups was approximately 350 and 400 days, respectively. Febuxostat was safe and generally well tolerated at doses of 80 mg, 120 mg and 240 mg (two times the maximum clinical dose). Adverse drug reactions (ADRs) were mostly mild or moderate in severity. The worldwide post-marketing experience confirmed the safety of febuxostat in the gout and adult TLS setting [31]. In the phase III FLORENCE study [30] comparing febuxostat to allopurinol for the prevention of hyperuricemia in adult patients with hematologic malignancies at intermediate to high risk for TLS, 173 patients were exposed to febuxostat 120 mg for a mean time of approximately 7 days. No safety concerns raised from febuxostat treatment. Adverse drug reactions (ADRs) occurred with the same incidence of allopurinol (6.4%) and, noteworthy, all febuxostat ADRs were mild or moderate in severity. Neither serious ADRs, nor study drug-related deaths occurred.

5) The pediatric febuxostat doses were selected based on predicted exposures (C_{max} and AUC) which were considered to be safe (i.e., exposure not greater than that observed in adults receiving 240 mg dose in previous clinical studies), and efficacious (i.e., febuxostat exposure following a 120 mg dose to adults was effective in controlling sUA levels throughout the chemotherapy treatment period).

6) In order to reduce any risk or discomfort associated with blood sampling in children and adolescents, a population PK design allowing to minimize the number of blood samples has been adopted.

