7. STUDY OBJECTIVES

7.1 PRIMARY OBJECTIVE

The primary objectives of this trial are:

- To assess the pharmacokinetics (PK) of febuxostat in pediatric patients ($\geq 6 < 18$ years of age) and in adults suffering from hematological malignancies at intermediate to high risk of TLS.
- To compare the febuxostat exposure in pediatric patients ($\geq 6 < 18$ years of age) with the one achieved in adults administered with a dose of 120 mg/QD.

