8.2 DISCUSSION OF STUDY DESIGN, INCLUDING THE CHOICE OF CONTROL GROUP

The present phase I/II trial has been designed taking into account the relevant published literature, available scientific guidelines and recommendations, standard clinical practice and the results of the phase III FLORENCE study [30] in adults. The study has been designed in order to avoid/minimize inappropriate exposure to non efficacious/non safe febuxostat doses in the pediatric population, as per guideline CHMP/EWP/147013/2004 [33].

The study outline was part of the febuxostat Pediatric Investigational Plan (PIP) agreed with the Pediatric Committee of the European Medicines Agency [32] and endorsed by the EMA [17].

The primary objective of this phase I/II study is to assess the pharmacokinetics (PK) of febuxostat in

pediatric patients ($\geq 6 < 18$ years of age) in order to ascertain that the systemic exposure attained with the selected doses is comparable to that achieved in adults administered with a dose of 120 mg/QD. The secondary objectives are to compare the pharmacokinetic/pharmacodynamics (PK/PD) and safety of febuxostat between pediatric patients (≥ 6 and < 18 years) and adults. The required sample size encompasses approximately 24 patients per treatment dose in children and adolescents groups, and ≈ 24 patients in the adults group. The choice of the 120 mg once daily febuxostat dosage for adults resembles that already successfully and safely used in the phase III FLORENCE study [30], whereas two different febuxostat dosages, both expected to result in an exposure to febuxostat not exceeding that seen with 240 mg once daily in adults, will be tested in each pediatric subset of patients in order to allow a PK study of febuxostat in the target population.

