9.3.4 Secondary analysis

- ***Pharmacodynamic endpoint:***

Area under plasma uric acid concentration curves (AUC sUA_{1-8}) from baseline (Visit 1, Day 1) to the Evaluation Visit (Visit 8, Day 8) will be computed for dose and age group using a trapezoidal rule which approximates the integral or the area under a curve.

A graphic example is provided in order to show which is the area considered to calculate AUC.

Figure 1

The trapezoidal rule is a numerical method to be used to approximate the integral or the area under a curve. Trapezoidal rule first involves dividing the area into a number of strips of equal width, with low limit identified with a and upper limit with b. Then, approximating the area of each strip by the area of the trapezium formed and summing these approximations, the final numerical result will be the area under the curve.

The trapezoidal rule will be presented by mean of a definite integral:

$$\int_a^b f(x)dx$$

Last observation carried forward method (LOCF) will be applied for patients who discontinued the study prematurely and a linear interpolation method will be used to impute the missing data between visits.

The pharmacodynamic analysis will be run on PK population and for exploratory reasons on ITT population.

- ***PK/PD endpoint:***

Observed exposure-response data will be descriptively and graphically summarized by age and dose group.

The aim of this analysis is to support the assumption of a comparable PK/PD relationship between pediatric patients ($\geq 6 < 18$ years of age) and adults and to evaluate if potential deviations in PK are clinically relevant.

This analysis will be conducted on the PK population.

- ***Clinical endpoints: Incidence of LTLS and CTLS***

- The assessment for LTLS from Start of Chemotherapy (Visit 3, Day 3) to the Evaluation Visit (Visit 8, Day 8) will be defined as:

1: PRESENCE 2 or more laboratory abnormalities including: a 25% increase or levels above normal for serum uric acid, potassium, and phosphate or a 25% decrease or levels below normal for calcium.

0: ABSENCE less than 2 laboratory abnormalities including: a 25% increase or levels above normal for serum uric acid, potassium, and phosphate or a 25% decrease or levels below normal for calcium.

- The assessment for CTLS from Start of Chemotherapy (Visit 3, Day 3) to the Evaluation Visit (Visit 8, Day 8) is defined as:

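### Readable section 9.3.3 aims to demonstrate similar exposure from a descriptive comparison of group summaries, and names no paediatric/adult ratio or interval as the basis

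*Combined protocol and SAP*

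**What the plan says.** Section 7.1 lists the comparison as a primary objective: "To compare the febuxostat exposure in pediatric patients" with exposure in adults on 120 mg once daily. Section 8.2 gives its purpose: "in order to ascertain that the systemic exposure attained with the selected doses is comparable to that achieved in adults". Section 6.1 says what depends on it: the adult phase III efficacy and safety data "will be bridged to the pediatric population by solely PK, as well as by PK/PD analyses".

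The readable method in section 9.3.3 has two steps. PK results are summarised by dose and age group, with statistics that include "geometric mean, 95% confidence intervals, coefficient of variation (CV%), median, minimum, and maximum". Then relevant parameters such as AUC and Cmax in the paediatric groups "will be descriptively compared to those in adults to demonstrate sufficient similarity of febuxostat pharmacokinetics". The PK population is primary and the PP-PK population exploratory.

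Related elements stand elsewhere. Section 6.1 plans modelling "in order to investigate the relationship between PK/PD and age as main covariate". Section 9.3.2 fits all age groups by nonlinear mixed-effects methods. The PK/PD analysis in section 9.3.4 is meant, among other things, "to evaluate if potential deviations in PK are clinically relevant". Section 6.3 justifies the paediatric doses partly by "exposure not greater than that observed in adults receiving 240 mg dose in previous clinical studies".

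**The concern.** Demonstrating similarity is a conclusion about the difference between two groups. The readable method describes each group and then compares them descriptively. It does not name the quantity that expresses the difference (a ratio of exposures), nor say how its uncertainty will be stated. By contrast, section 9.3.4 names a between-group test for the secondary LTLS and CTLS endpoints.

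What is at stake is how the main result will be worded. If 9.3.3 is followed as it reads, the report could call the exposures sufficiently similar without showing how large a paediatric/adult difference the data still allow. The PK/PD step in 9.3.4 does not fill this gap: it judges whether deviations in PK matter, which presupposes that the deviation has been estimated.

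**Working it through.** **The plan's own figure.** Section 9.1 and the synopsis give about 24 patients in each of five groups and about 135 screened at 10% screening failure. 5 × 24 = 120, and 120 / 0.90 = 133.3, which rounds up to 134. This agrees with the stated approximate 135. The reason for 24 per group cannot be read, so no precision target can be checked.

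**Where a contrast might stand.** In 9.3.3, the 95% confidence intervals appear only in the list of statistics by dose and age group. Readable 9.3.1 gives general descriptive statistics. Readable 9.3.2 describes estimation of population and individual parameters. Readable 9.3.4 summarises exposure-response data by group. None gives a paediatric/adult exposure ratio or difference. Section 6.1 names age as main covariate but defines no exposure contrast from the model.

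**What the group statistics already allow.** With n, geometric means and CV% for two groups, a reader can form

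- ratio = geometric mean (paediatric cohort) / geometric mean (adults);
- s = sqrt(ln(1 + CV²)), the SD on the log scale, taken as equal in the two groups;
- SE of the log ratio = s × sqrt(2/24), with 46 degrees of freedom;
- 90% limits = ratio divided and multiplied by exp(t(0.95, 46) × SE), with t = 1.679.

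So the information for an approximate ratio is planned. What is absent is its designation as the basis of the conclusion.

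**Precision of such a ratio (illustration).** The documents give no readable between-patient CV for AUC or Cmax, so 30% to 60% is assumed. The observed ratio is set to 1.00. For comparison, the 95% factor for one group's own geometric mean is exp(t(0.975, 23) × s / sqrt(24)), with t = 2.069. The 95% factor for the ratio uses t(0.975, 46) = 2.013.

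| CV | s | SE of log ratio | 90% factor, ratio | 90% CI at ratio 1.00 | 95% factor, one group | 95% factor, ratio |
|---|---|---|---|---|---|---|
| 30% | 0.294 | 0.085 | 1.153 | 0.87–1.15 | 1.132 | 1.186 |
| 40% | 0.385 | 0.111 | 1.205 | 0.83–1.21 | 1.177 | 1.251 |
| 50% | 0.472 | 0.136 | 1.257 | 0.80–1.26 | 1.221 | 1.316 |
| 60% | 0.555 | 0.160 | 1.308 | 0.76–1.31 | 1.264 | 1.380 |

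At the same 95% level, the interval for the ratio is wider than either group's own interval. A display of group intervals alone therefore does not show the uncertainty of the comparison directly. An interval from the Pop-PK model would differ somewhat from these figures.

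**The case against.** The strongest objection is that the absence falls where text has been removed. The sample-size rationale in 9.1 breaks off mid-sentence, the primary-endpoint text of 8.8.1 and the synopsis account of the PK analysis cannot be read, 9.3.2 is very short, and an image is missing at the end of 9.3.3. Section 9.5 leaves detail to a SAP whose text is not readable here. This stands as a limit: a reader might infer that the plan has no exposure contrast at all, and the documents do not support that. It does not change the 9.3.3 sentence that can be read, which states its method and the claim to be drawn from it.

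Second, a reader might infer that a similarity statement would rest on no measure of the difference. That is too strong. The planned group statistics yield an approximate ratio and interval, and an age effect in the model would itself be a paediatric/adult contrast.

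Third, one can compute that two groups' own 95% intervals still touch at observed ratios of 1.28 (CV 30%) to 1.60 (CV 60%), where a 90% CI on the ratio excludes 1. This should not be held against the plan. It states no overlap rule, and excluding 1 shows a difference, not a lack of sufficient similarity. Those ratios also lie below the exposure at 240 mg in adults, the upper reference for dose choice, which is at least twice the 120 mg AUC under either account of dose proportionality in the documents (section 6.2.1 and the 120 mg SmPC, section 5.2).

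Finally, this is an open-label phase I/II study that section 6.3 describes as exploring the PK/PD profile. A descriptive primary comparison is defensible there. The mismatch lies in the claim to demonstrate similarity from it.

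**Conclusion.** The point holds in limited form, with medium confidence because of the redactions. As readable, section 9.3.3 sets a descriptive comparison of group-level summaries against a claim to demonstrate similarity, and does not name a paediatric/adult ratio or interval as the basis, although the comparison is a primary objective that supports the bridge to children.

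The illustrated 90% CI, 0.87–1.15 to 0.76–1.31 at an observed ratio of 1.00, rests on 24 patients per group, log-normal exposure with equal variance, and an assumed CV of 30% to 60%. It indicates scale only and does not show that the study is too small. Nor would an interval by itself demonstrate similarity: that needs a criterion fixed in advance, and none is readable in 9.3.3.

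**What to change.** In section 9.3.3, state that for each paediatric cohort against adults on 120 mg the geometric mean ratio of AUC(0-tau) and Cmax will be reported with a CI, for example 90%. Take it from the Pop-PK model, or from individual estimates with shrinkage reported. Base the similarity wording on that interval, read together with the PK/PD assessment in 9.3.4. If blacked-out text or the SAP already holds such a contrast, name it in 9.3.3 as the basis. Unless a similarity criterion is pre-specified, reword the aim from demonstrating sufficient similarity to estimating and describing it.

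The cost is a little analysis code; no patients, visits or samples are added. The resulting statement may be less favourable. Under section 9.5, a substantial amendment may be needed if this counts as a change to the primary analysis; otherwise SAP wording is enough. The interval covers sampling error only. The groups are not randomised, so differences in case mix between children, adolescents and adults remain outside it and should be stated as a limitation.

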9.3.4 Secondary analysis

- ***Pharmacodynamic endpoint:***

Area under plasma uric acid concentration curves (AUC sUA_{1-8}) from baseline (Visit 1, Day 1) to the Evaluation Visit (Visit 8, Day 8) will be computed for dose and age group using a trapezoidal rule which approximates the integral or the area under a curve.

A graphic example is provided in order to show which is the area considered to calculate AUC.

Figure 1

The trapezoidal rule is a numerical method to be used to approximate the integral or the area under a curve. Trapezoidal rule first involves dividing the area into a number of strips of equal width, with low limit identified with a and upper limit with b. Then, approximating the area of each strip by the area of the trapezium formed and summing these approximations, the final numerical result will be the area under the curve.

The trapezoidal rule will be presented by mean of a definite integral:

$$\int_a^b f(x)dx$$

Last observation carried forward method (LOCF) will be applied for patients who discontinued the study prematurely and a linear interpolation method will be used to impute the missing data between visits.

The pharmacodynamic analysis will be run on PK population and for exploratory reasons on ITT population.

- ***PK/PD endpoint:***

Observed exposure-response data will be descriptively and graphically summarized by age and dose group.

The aim of this analysis is to support the assumption of a comparable PK/PD relationship between pediatric patients ($\geq 6 < 18$ years of age) and adults and to evaluate if potential deviations in PK are clinically relevant.

This analysis will be conducted on the PK population.

- ***Clinical endpoints: Incidence of LTLS and CTLS***

- The assessment for LTLS from Start of Chemotherapy (Visit 3, Day 3) to the Evaluation Visit (Visit 8, Day 8) will be defined as:

1: PRESENCE 2 or more laboratory abnormalities including: a 25% increase or levels above normal for serum uric acid, potassium, and phosphate or a 25% decrease or levels below normal for calcium.

0: ABSENCE less than 2 laboratory abnormalities including: a 25% increase or levels above normal for serum uric acid, potassium, and phosphate or a 25% decrease or levels below normal for calcium.

- The assessment for CTLS from Start of Chemotherapy (Visit 3, Day 3) to the Evaluation Visit (Visit 8, Day 8) is defined as:

1: PRESENCE presence of LTLS in addition to 1 or more of the following significant clinical complications: renal insufficiency, cardiac arrhythmias, sudden death and seizures.

0: ABSENCE absence of LTLS or absence of any significant clinical complications: renal insufficiency, cardiac arrhythmias, sudden death and seizures.

Chi Square test will be used to compare statistically the rate incidence of LTLS and CTLS by dose and age group.

The efficacy analyses will be run on the ITT population and for exploratory reasons on PP-population.

- ***Assessment of the age-appropriate formulation acceptability***

Assessment of the age-appropriate formulation acceptability will be evaluated through a 5-point

hedonic scale anchored with the word super bad and super good and summarized by means of descriptive statistics by febuxostat dose in children. The analysis will be conducted on the safety population.

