
Sample size
	
A sample size of approximately 24 patients will be included in the Pharmacokinetic population for each age and dose group (pediatric cohorts 1-4 and adults).
 

 
Assuming a 10% screening failure rate, around 135 patients should be screened in order to enroll approximately a total

to Day 8 (AUC sUA₁₋₈). Comparisons will be made between febuxostat doses among the age groups and carried out on ITT and PK population.

- PK/PD: observed exposure-response data will be descriptively and graphically summarized by age and dose group. [REDACTED]

[REDACTED]

The aim of this analysis is to support the assumption of a comparable PK/PD relationship between pediatric patients ($\geq 6 < 18$ years of age) and adults and to evaluate if potential deviations in PK are clinically relevant. This analysis will be conducted on PK population.

[figure not shown]
- Clinical: incidence of LTLS and CTLS will be summarized through descriptive statistics by febuxostat dose and age group and their statistical comparison will be performed using a Chi Square test. Clinical endpoint analyses will be run on ITT population and for exploratory reasons on PP-population.
- Safety:
 - adverse events will be coded using the MedDRA dictionary. The incidence, severity, seriousness and causality of each TESS will be summarized by system organ class, preferred term by febuxostat dose and age group;
 - reasons for early termination will be summarized by febuxostat dose and age group;
 - laboratory findings and changes in PS will be reported by febuxostat dose and age group.All safety analyses will be run on the safety population.
- Assessment of the age-appropriate formulation

	
acceptability will be evaluated through a patient diary and summarized by means of descriptive statistics by febuxostat dose in children. The analysis will be conducted on the safety population.

--	---

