7.2 SECONDARY OBJECTIVES

The secondary objectives of this trial are:

- To compare the pharmacodynamics (PD) of febuxostat between pediatric patients ($\geq 6 < 18$ years of age) and adults.
- To evaluate and compare the PK/PD relationship of febuxostat in pediatric patients ($\geq 6 < 18$ years of age) and adults.
- To evaluate the safety of febuxostat between pediatric patients ($\geq 6 < 18$ years of age) and adults.
- To evaluate the occurrence of Laboratory TLS (LTLS) and Clinical TLS (CTLs) according to Cairo and Bishop Criteria (see Appendix I: Definition of LTLS and CTLs).
- To assess the age-appropriate formulation acceptability in children.

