8.3.1 Inclusion criteria

male and female children of 6 to less than 12 years of age, adolescents of 12 to less than 18 years of age and adults from 18 years:

- a. scheduled for first cytotoxic chemotherapy cycle, regardless of the line of treatment, because of hematologic malignancies, and
- b. at intermediate or high risk of TLS [4], and
- c. with serum uric acid (sUA) levels < 10 mg/dL at Visit 1 (Day 1), and
- d. with no access to rasburicase;

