8.5 TREATMENTS

8.5.1 Treatment Allocation

The study will be performed according to an open design; no blinding technique will be adopted.

Eligible patients will receive study treatment at Visit 1 (Day 1) after completing the relevant “prior to drug administration” procedures and re-checking of the eligibility criteria.

The IMP box assignment will be performed by means of the IxRS system (see section 10.1.2) without any randomized allocation. The first ≈24 children will be allocated to the 40 mg dose, the following ≈24 children to the 60 mg dose. The first ≈24 adolescents will be allocated to the 80 mg dose, the following ≈24 adolescents to the 120 mg dose. The ≈24 adults will be allocated to the 120 mg dose.

For children, the 20 mg febuxostat tablets will be used, whereas for adolescents and adults the market product ADENURIC® 80 mg and 120 mg will be employed as represented below:

Table 1. Febuxostat: Treatment dose and form

Patient Population	Treatment dose	Treatment form
Children	febuxostat 40 mg	2 tablets 20 mg
	febuxostat 60 mg	3 tablets 20 mg
Adolescents	ADENURIC® 80 mg	1 tablet 80 mg

	ADENURIC® 120 mg	1 tablet 120 mg
Adults	ADENURIC® 120 mg	1 tablet 120 mg

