8.6.1.2 Visit 1, Start of Treatment (Day 1)

Start of Treatment Visit will be performed 2 days prior to the scheduled chemotherapy. During the Start of Treatment Visit, the following procedures will be performed:

Prior to the drug administration:

- record of adverse events and change in concomitant medication;
- re-check of inclusion/exclusion criteria and patient's eligibility confirmation;
- physical examination and vital signs;
- KPS/LPS evaluation;
- blood sampling and urine collection for safety laboratory tests (**NOTE:** safety laboratory tests performed within 24 hours do not need to be repeated at Visit 1, Day 1);
- blood sampling for centralized laboratory test (sUA); whenever possible blood sampling for centralized laboratory test (sUA) will be collected in conjunction with safety laboratory tests to reduce the patient's discomfort of additional venopunctures;
- assessment of LTLS/CTLS;
- allocation of investigational medicinal product (IMP) treatment box as per IxRS assignment.

Study drug administration:

- administration of febuxostat as per age group.

After study drug administration:

- assessment of the age-appropriate formulation acceptability (only for children).

NOTE: Screening Visit and Visit 1 (Day 1) may occur on the same day. Common assessments will be performed only once.

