8.6.2.3 Centralized Laboratory Evaluation for Pharmacodynamic Parameter

At each Visit starting from Visit 1 (Day 1) until Evaluation Visit (Visit 8, Day 8), a centralized laboratory test (sUA) will be used for pharmacodynamic parameter sUA. Whenever possible, sampling will be collected in conjunction with safety laboratory tests to reduce the patient's discomfort of additional venopunctures. All samples for centralized laboratory test will be processed at the site and the serum shipped to be centrally analyzed at the Central Laboratory.

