9.3 STATISTICAL ANALYSIS

9.3.1 Descriptive statistics

[figure not shown]
[figure not shown]
All study variables will be presented by dose and age group, by using the appropriate descriptive statistics according to the variable nature, unless otherwise specified:

[figure not shown]
- Continuous variables: number of non-missing observations, mean, standard deviation, standard error of the mean, minimum, median, maximum.
- Categorical variables: number of non-missing observations and column percentages (N, %).

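### No visible text uses pre-dose Day 1 serum uric acid in the non-randomised comparison of AUC sUA(1-8), although it is collected and is the first point of the AUC

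*Combined protocol and SAP*

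**What the plan says.** Section 7.2 sets a secondary objective: "To compare the pharmacodynamics (PD) of febuxostat between pediatric patients" and adults. The synopsis adds, for AUC sUA(1-8): "Comparisons will be made between febuxostat doses among the age groups and carried out on ITT and PK population". Section 8.5.1 assigns treatment "without any randomized allocation": cohort follows from age and, within children and adolescents, from order of entry.

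Section 9.3.4 starts the AUC at Visit 1, Day 1, ends it at Day 8, and states that it "will be computed for dose and age group using a trapezoidal rule which approximates the integral or the area under a curve". It adds LOCF after early discontinuation, linear interpolation for gaps between visits, and the analysis population. No covariate, change-from-baseline version or model for the AUC is visible.

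The baseline value exists. Section 8.6.1.2 lists, among the steps before dosing, "blood sampling for centralized laboratory test (sUA"). Section 8.6.2.3 says that from Visit 1 to Visit 8 "a centralized laboratory test (sUA) will be used for pharmacodynamic parameter sUA". Section 9.3.1 says "All study variables will be presented by dose and age group", which implies that Day 1 sUA will be tabulated by group.

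**The concern.** AUC sUA(1-8) reflects both where a patient starts and how far the drug lowers uric acid. In a randomised trial the starting level is balanced on average. Here nothing balances it. Section 8.3.1 admits patients with uric acid "levels < 10 mg/dL at Visit 1 (Day 1"), and section 8.2 places no restriction on type of haematological malignancy, so mean Day 1 sUA may differ between a paediatric cohort and adults.

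If it does, a raw AUC difference can look like a different drug effect, or conceal one. This is true of a descriptive comparison as well as of a test. Tabulating Day 1 sUA by group would reveal a gap but would not show how much of the AUC difference it explains.

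The endpoint carries some weight: section 6.1 describes it as the primary efficacy parameter of the adult pivotal study (FLORENCE) and plans to bridge adult results to children by PK and PK/PD analyses.

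**Working it through.** The documents state no effect size, margin or power for this comparison, so there is no figure of the plan's own to reproduce. The check is how far a Day 1 gap moves the AUC.

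**Inputs**
- Eight daily central sUA samples, Day 1 to Day 8 (section 8.6.2.3), taken as 24 h apart.
- Trapezoidal rule (section 9.3.4).
- Adult pivotal febuxostat mean AUC sUA(1-8): 514.0 mg·h/dL (Appendix II, 120 mg SmPC, section 5.1).
- Mean sUA reduction of 25-70% across doses in healthy subjects (section 6.2.2).
- Assumed: a Day 1 gap of d = 1 mg/dL, with 0.5 mg/dL as the alternative.

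**Step 1: weight of Day 1.** The weights are 12 h for Day 1, 24 h for each of Days 2-7, and 12 h for Day 8. The total is 12 + 6 × 24 + 12 = 168 h. Day 1 carries 12/168 = 7.1%, and Days 2-8 carry 156 h.

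**Step 2: shift from a gap.** Let c be the share of the gap that persists on Days 2-8. Then

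shift = d × (12 + 156c).

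With d = 1 the shift is 12 if the gap vanishes by Day 2 (c = 0) and 168 if it persists in full (c = 1).

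**Step 3: a guide to c.** If both groups have the same proportional reduction r at every sample on Days 2-8, then c = 1 − r.

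| r | c | shift, d = 1 | % of 514 | shift, d = 0.5 |
|---|---|---|---|---|
| 70% | 0.30 | 12 + 46.8 = 58.8 | 11.4% | 29.4 |
| 50% | 0.50 | 12 + 78.0 = 90.0 | 17.5% | 45.0 |

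The drug effect is identical in both groups in every row, so the whole shift comes from the starting level. The 70% row is the top of the healthy-subject range; the 50% row is an illustration.

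**Step 4: which adjustment fits.** Under proportional reduction, a patient with baseline b has AUC = b × (12 + 156(1 − r)). The slope of raw AUC on baseline is then 58.8 at r = 70% and 90.0 at r = 50%. It differs whenever drug effect differs, so a common-slope model on raw AUC breaks down in the case the comparison is meant to detect. On the log scale,

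log AUC = log b + log(12 + 156(1 − r)).

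The slope is 1 in every group whatever r is, and a difference in drug effect appears as a difference in intercept, that is, as a ratio of AUCs.

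**The case against.** **Text may be missing.** The start of the synopsis PD paragraph is lost, text may also be gone from 9.3.4 without a mark, and the SAP that section 9.5 announces is not available. A reader might infer that the plan has no baseline adjustment. The documents do not support that; they support only that none is visible. This objection stands and limits the point.

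**PK/PD modelling may cover it.** Section 6.1 plans modelling with age as the main covariate, which leaves room for others. The model text is not visible, so whether it handles baseline sUA is unknown. Such a model would also not by itself change how the group AUCs in 9.3.4 are compared.

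**No test is visible.** Section 9.3.4 names a chi-square test for LTLS and CTLS but none for AUC. A reader might infer an inflated false-positive rate; without a stated test, that does not follow. The shift in a descriptive difference remains.

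**The size is assumed.** The documents give no baseline sUA by age. The healthy-subject range is dose-dependent, so its 25% end is a doubtful guide for a comparison with adults on 120 mg, and the larger shift it would imply is not relied on here. Those subjects also had no chemotherapy. Entry is narrower than the 10 mg/dL limit suggests: LTLS at Visit 1 is an exclusion, so under Appendix I uric acid of 8 mg/dL or more with one further qualifying abnormality bars entry.

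**Precision.** A reader might expect narrower intervals. The documents do not establish this: the adult pivotal study used analysis of covariance, but its covariates are not named. No precision gain is claimed.

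**Conclusion.** The point holds for the visible text. AUC sUA(1-8) begins at a pre-dose value that is collected, the groups are not randomised, and nothing visible uses that value in the comparison. Each 1 mg/dL of Day 1 gap shifts the raw AUC difference by 12 + 156c mg·h/dL: about 59 (11% of the adult mean) at a common 70% reduction and 90 at 50%, and half of each for a gap of 0.5 mg/dL. These figures assume the gap, equal proportional reduction from Day 2 onward, and 24 h spacing.

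A reader might go further and conclude that the age comparison is invalid, or that adjusting for baseline would repair it. Neither follows. Whether a baseline gap will occur is unknown, and adjustment leaves confounding by malignancy, chemotherapy and order of entry in place. The endpoint is secondary and the primary PK comparison is untouched. It is a modest improvement worth making before database lock.

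**What to change.** First check the SAP and the unredacted text. Unless they already provide for it, pre-specify in the SAP one supportive baseline-adjusted comparison of each paediatric age/dose group with adults:

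- ANCOVA of log AUC sUA(1-8) on age/dose group and log Visit 1 central sUA, reporting adjusted ratios to adults with 95% CIs.
- The model fixed in advance, with no switch that depends on the data.
- Results shown beside the unadjusted AUC and Day 1 sUA by group, with a display of how far baselines overlap.
- A statement that the adjustment does not remove confounding by malignancy, chemotherapy or order of entry.

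The cost is SAP wording and slightly more analysis. No sample or visit is added. Section 9.5 lets changes outside the primary endpoint and analysis be detailed in the SAP alone, and treats analyses not pre-specified and run after database lock as exploratory, so the timing matters. The downside is reliance on overlapping baselines and on the model form: if reduction is not roughly proportional, for example because chemotherapy adds a uric acid load unrelated to baseline, the common log-scale slope is only an approximation. That is why the unadjusted result stays beside it.
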